### 3.5.3 Exploratory Efficacy Assessments

#### 3.5.3.1 PAGI-SYM

The PAGI-SYM questionnaire on gastroparesis symptoms is completed on Days 1 and 14 and includes 6 subscales: heartburn/regurgitation, fullness/early satiety, nausea/vomiting, bloating, upper abdominal pain, and lower abdominal pain. The total and subscale scores will be derived based on the PAGI-SYM Information Booklet (section 5, 2nd Edition, 2015). Both total and subscale PAGI-SYM scores, along with change from baseline and percent change from baseline, will be summarized by treatment group.

#### 3.5.3.2 Clinical Grading Assessment Scale

For assessment of global clinical response, the following question will be utilized at Day 14: "In thinking about the last 2 weeks, how would you say your stomach/gastroparesis-related problems/symptoms have been compared to the period before you started treatment on this study?" Responses will be: improved, no change, or worsened. Subjects will be asked to quantify their therapeutic response using the Clinical Patient Grading Assessment Scale (CPGAS). Subjects will pick a number over a range (+7 = completely better; 0 = no change; -7 = very much worse) that best answers the question. The investigator will complete the same assessment based on their judgment of the subject's response to treatment. Responses and CPGAS (subject and Investigator) scores will be summarized by treatment group.

## 3.6 Pharmacokinetic Assessments

### 3.6.1 Sample Collections for Pharmacokinetic Analysis

For all subjects, blood samples for PK analysis will be collected at the following visits and timepoints:

- Day 1: [REDACTED] prior to and [REDACTED] after the morning dose
- Days 3 [ $\pm 1$  day], 7 [ $\pm 1$  day], and 10 [ $\pm 1$  day]: [REDACTED] prior to the morning dose
- Day 14 [ $\pm 2$  days]: [REDACTED] prior to the morning dose and [REDACTED] after the morning dose on
- Day 15 or Day 16 (+1 day)

Subjects may consent to participate in a more intensive PK subgroup. In this subgroup, PK samples will also be collected as follows:

- Day 1: [REDACTED] after the morning dose
- Day 14 ( $\pm 2$  days): [REDACTED] after the morning dose
- Day 15
- Day 16 (+1 day)

Note: in some situations, collection of specific, individual PK samples [REDACTED] may not be required in this subset of subjects with prior written sponsor approval.

### 3.6.2 Handling Missing or Below the Lower Limit of Quantification Data

For PK concentration data, if the actual sampling time is missing, but a valid concentration value has been measured, the concentration value will be flagged, and the scheduled time point may be used for the calculation of PK parameters.

In cases of missing pre-dose for each treatment, the missing components may be assumed as zero. For the other missing predose cases beyond first dose, the missing data will not be imputed.

For the individual concentration and PK parameter calculation of each treatment, the following rules will be applied:

- If one or more BLQ values occur before the first measurable concentration, they will be assigned a value of zero.
- If BLQ values occur between measurable concentrations in a profile, the BLQ should be omitted (set to missing).
- If BLQ values occur after the last measurable concentration in a profile, the BLQ should be omitted (set to missing).

For the concentration summary and mean concentration plot preparation of each treatment, the following rules will be applied:

- Mean concentration at any individual time point will only be calculated if at least half of the subjects have valid values (i.e. quantifiable and not missing) at this time point for each treatment.
- In cases where a mean value is not calculated due to the above criterion not being met, the value will be set to missing.
- BLQ values will be set to zero.

### 3.6.3 Pharmacokinetic Concentration

Individual plasma concentrations of deuterated domperidone will be summarized by treatment at each nominal time point for the PK Population descriptively. Individual plasma concentrations will also be listed for the PK Population.

Individual plasma concentration will be plotted by treatment on a linear and semi-log scale against actual sampling time points relative to dosing time. Mean ( $\pm$ SD) concentration will be plotted on a linear and semi-logarithmic scale against nominal time points by treatment, when available. LLOQ will be plotted as a reference line in both instances. Trough concentrations will be presented in a similar manner using predoses on Days 7, 10, and 14.

Actual sampling times that are outside the sampling time windows may be excluded from concentration summary and mean concentration plotting but will still be used in the calculations of PK parameters and individual concentration plotting. The following windows will be permitted for the collection of PK samples:  $\pm 2$  minutes for samples collected  $\leq 2$  hours postdose and  $\pm 5$  minutes for samples collected  $> 2$  hours postdose.

Trough concentrations collected throughout the study will be used to confirm compliance and attainment of steady-state.

### 3.6.4 Pharmacokinetic Parameters

The following PK parameters will be calculated for deuterated domperidone (and any measured metabolites) using plasma concentrations (Day 1) using a noncompartmental method if the data permit:

Parameters	Description
$C_{max}$	Maximum plasma concentration; determined directly from the concentration time profile; if the maximum plasma concentration occurs at more than one time point, $C_{max}$ is defined as the first maximum value
$T_{max}$	Time to $C_{max}$ ; If the maximum value occurs at more than one time point, $T_{max}$ is defined as the first time point with this value.
$AUC_{0-12}$	Area under the concentration-time curve (AUC) from predose (time 0) to 12 hours

The following PK parameters will be calculated for deuterated domperidone (and any measured metabolites) using measured plasma concentrations following the final dose of CIN-102 (AM of Day 14), if the data permit:

Parameters	Description
$C_{max}$	Maximum plasma concentration; determined directly from the concentration time profile; if the maximum plasma concentration occurs at more than one time point, $C_{max}$ is defined as the first maximum value
$T_{max}$	Time to $C_{max}$ ; If the maximum value occurs at more than one time point, $T_{max}$ is defined as the first time point with this value.
$AUC_{tau}$	AUC over the dosing interval; calculated using the trapezoidal method
$AUC_{0-t}$	Area under the plasma concentration vs time curve (AUC) from predose (time 0) to the last quantifiable plasma concentration ( $C_{last}$ )
$AUC_{0-inf}$	AUC from time 0 to infinity; calculated as $(AUC_{0-t} + C_{last}/\lambda_z)$
$AUC\%_{extrap}$	Percent of $AUC_{0-inf}$ extrapolated, represented as $(1 - AUC_{0-t}/AUC_{0-inf}) \times 100$
$\lambda_z$	Apparent first-order terminal elimination rate constant calculated from a semi-log plot of the plasma concentration versus time curve. The parameter will be calculated by linear least-squares regression analysis using points in the terminal log-linear phase.
$T_{1/2}$	Apparent first-order terminal elimination half-life; calculated as $\ln(2)/\lambda_z$
$CL/F$	Apparent total plasma clearance after oral administration; calculated as $Dose/AUC_{0-inf}$
$V_z/F$	Apparent volume of distribution during terminal elimination phase after oral administration; calculated as $Dose/[\lambda_z \times AUC_{0-inf}]$
$R_{Cmax}$	Accumulation ratio based on $C_{max}$ after the first dose and the final dose; calculated as $C_{max, D14}/C_{max, D1}$
$R_{AUC}$	Accumulation ratio based on $AUC_{tau}$ after the first dose and last dose; calculated as $AUC_{0-tau, D14}/AUC_{tau, D1}$

Actual collection times will be used in PK parameter calculations. The Linear-Log Trapezoidal method (equivalent to the Linear Up/Log Down option in WinNonlin) will be used in the computation of all AUC values. In order to estimate the apparent first-order terminal elimination constant,  $\lambda_z$ , linear regression of concentration in logarithm scale vs. time will be performed using at least 3 data points. Uniform weighting will be selected to perform the regression analysis to estimate  $\lambda_z$ . The constant  $\lambda_z$  will be assigned but flagged if one of the following occurs:

1. the terminal elimination phase is not linear (as it appears on a semi-logarithmic scale)
2. the terminal elimination rate constant indicates a positive slope ( $\lambda_z > 0$ )
3.  $T_{max}$  is one of the 3 last data points
4. the adjusted regression coefficient ( $R^2$ ) is less than 0.8
5. The  $AUC_{\%extrap}$  exceeds 20%

These  $\lambda_z$  values and  $\lambda_z$ -derived parameters will be listed but excluded from statistical analysis.

No value for  $\lambda_z$ ,  $AUC_{0-inf}$ ,  $AUC_{\%extrap}$ ,  $CL/F$ ,  $V_z/F$ , or  $T_{1/2}$  will be reported for cases that do not exhibit an acceptable terminal log-linear phase in the concentration-time profile.

No PK parameters will be calculated for subjects with 2 or fewer detectable concentrations in their PK profile.

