#### 7.4 Pharmacokinetics

For all subjects, blood samples for PK analysis will be collected at the following visits and timepoints:

- [REDACTED]
- [REDACTED]
- [REDACTED]
- [REDACTED]

Subjects may consent to participate in a more intensive PK subgroup. In this subgroup, PK samples will also be collected as follows:

- [REDACTED]
- [REDACTED]
- [REDACTED]
- [REDACTED]

Note: in some situations, collection of specific, individual PK samples [REDACTED] may not be required in this subset of subjects with prior written sponsor approval.

[REDACTED]

The following PK parameters will be calculated for deuterated domperidone (and any measured metabolites) using plasma concentrations measured following CIN-102 doses on Day 1 if the data permit:

- $C_{\max}$
- Time to maximum plasma concentration

- AUC 0-12 hours

The following PK parameters will be calculated for deuterated domperidone (and any measured metabolites) using plasma concentrations measured following the final dose of CIN-102, if the data permit:

- $C_{\max}$
- Time to maximum plasma concentration
- AUC over a dosing interval
- AUC from time 0 to the time of the last quantifiable plasma concentration
- AUC from time 0 to infinity
- Percent of AUC extrapolated
- $T_{1/2}$
- Apparent plasma clearance
- Apparent volume of distribution

Trough concentrations collected throughout the study will be used to confirm compliance and attainment of steady-state.

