#### *2.3.4 Pharmacokinetic Variables*

The PK variables are concentrations and derived PK parameters of deuterated domperidone following multiple doses of CIN-102.

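### SAP 3.6.4 and protocol 7.4, read literally, apply CL/F and Vz/F to any measured metabolite using the CIN-102 dose, which mixes metabolite formation with elimination

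*SAP*

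**What the plan says.** SAP 3.6.4 has one list of parameters for the period after the Day 14 morning dose. Its lead-in reads "The following PK parameters will be calculated for deuterated domperidone (and any measured metabolites) using measured plasma concentrations following the final dose of CIN-102". The rows of that list that matter here are:

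- AUC0-inf, the observed AUC0-t with the extrapolated tail Clast/lambda_z added.
- CL/F, the dose divided by AUC0-inf.
- Vz/F, the dose divided by the product of lambda_z and AUC0-inf.

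No row is limited to the parent. There is no term for the fraction converted and no conversion to molar units. The lambda_z flags and reporting exclusions that follow the list do not distinguish analytes.

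Protocol 7.4 has the same scope, "The following PK parameters will be calculated for deuterated domperidone (and any measured metabolites) using plasma concentrations measured following the final dose of CIN-102", and its list also includes apparent clearance and apparent volume.

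Elsewhere the SAP speaks only of the parent. SAP 2.3.4 says "The PK variables are concentrations and derived PK parameters of deuterated domperidone following multiple doses of CIN-102", and the concentration summaries in SAP 3.6.3 are for deuterated domperidone. The visible text names no metabolite.

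**The concern.** Dose over AUC gives an apparent clearance when the dose and the AUC belong to the same compound. For a metabolite they do not. The dose is CIN-102, and the amount of metabolite entering the circulation is an unknown part of it. A table headed metabolite CL/F would therefore carry a number that depends on how much metabolite was formed as well as on how fast it was cleared.

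What is at stake is interpretation. Characterising PK is a listed objective, and protocol 1.3 says the results will support dose selection. A difference in metabolite CL/F between dose groups or subjects could come from a change in formation and be read as a change in elimination. The documents do not contain what would be needed to separate the two afterwards.

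**Working it through.** The plan states no figure that depends on these formulas, so there is nothing to reproduce. The check derives what the stated rule returns for a metabolite.

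**Inputs from the documents**
- The CL/F, Vz/F and AUC0-inf formulas (SAP 3.6.4).
- The final dose is the Day 14 morning dose. On a twice-daily schedule that is 13 x 2 + 1 = 27 doses.
- Oral bioavailability of undeuterated domperidone is about 13% to 17% (protocol 1.1), used only as a proxy for F.
- Protocol 1.4 gives doses in mg and concentrations in ng/mL.

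**Assumptions, not in the documents**
- Linear kinetics, one compartment each for parent and metabolite, molar units.
- fm (fraction of parent converted) 0.1 to 0.9.
- Parent half-life 4 to 20 h, parent clearance 40, metabolite clearance CLm 30, metabolite volume Vm 200, absorption rate 1/h.
- F = 0.15, except 0.13 to 0.17 in the first-pass case.

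The comparator is CLm/F, the most natural reading of the label CL/F.

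**Step 1. Simplest case.** With no presystemic formation, and either single-dose AUC0-inf or steady-state AUCtau,

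AUCm = F x fm x Dose/CLm, so Dose/AUCm = CLm/(F x fm).

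The ratio to CLm/F is 1/fm. Formation and elimination appear as one quotient and cannot be separated from plasma data after CIN-102 alone.

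**Step 2. The SAP's rule.** The SAP takes AUC0-inf after the last of repeated doses, so it includes metabolite still to come from earlier doses. The ratio becomes (1/fm) divided by the metabolite's AUC0-inf/AUCtau. For 12-hourly dosing without presystemic formation:

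| Parent half-life | AUC0-inf/AUCtau, metabolite | fm 0.3 | fm 0.5 | fm 0.9 |
|---|---|---|---|---|
| 4 h | 1.621 | 2.06 | 1.23 | 0.69 |
| 8 h | 2.099 | 1.59 | 0.95 | 0.53 |
| 12 h | 2.580 | 1.29 | 0.78 | 0.43 |
| 20 h | 3.542 | 0.94 | 0.57 | 0.31 |

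Example: (1/0.5)/1.621 = 1.23. Eight of the twelve entries are below 1. The once-daily arm in the SAP was not modelled for the metabolite; its carry-over would be smaller.

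**Step 3. First-pass formation, single dose.** Suppose all drug is absorbed and a share fm of the first-pass loss also becomes metabolite. Then AUCm = Dose x [(1 - F) x fm + F x fm]/CLm = Dose x fm/CLm, and the ratio to CLm/F is F/fm.

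| fm | F = 0.13 | F = 0.17 |
|---|---|---|
| 0.1 | 1.30 | 1.70 |
| 0.3 | 0.43 | 0.57 |
| 0.5 | 0.26 | 0.34 |
| 0.9 | 0.14 | 0.19 |

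**Step 4. Units.** If dose and AUC stay in mass units, every ratio above is multiplied by the parent-to-metabolite molecular-weight ratio. The documents do not give it.

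**Step 5. Vz/F.** Vz/F moves with CL/F only if lambda_z is the metabolite's own elimination rate. If formation is the slow step, lambda_z is the parent's rate, which adds a factor km/kp. With the assumed values km = 30/200 = 0.15/h. At a 20 h parent half-life kp = ln(2)/20 = 0.0347/h, so km/kp = 4.33. For fm 0.5 under the SAP's rule, the CL/F ratio is 0.565 and the Vz/F ratio is 0.565 x 4.33 = 2.45. One is too low while the other is too high.

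**Step 6. What can be estimated.** In the simplest case, the molar ratio of steady-state AUCtau is AUCm/AUCp = fm x CLp/CLm. F and the dose cancel. It still combines formation and elimination, but as an exposure ratio it claims nothing more.

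**The case against.** The strongest case against acting has three parts.

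1. *The premise is conditional.* The lists cover metabolites only if they are measured and the data allow. The visible text names none, and the PK variables, concentration summaries and PK populations refer only to the parent or CIN-102. A redacted block precedes the parameter list in protocol 7.4, and its content cannot be judged. This stands: without a metabolite assay there is no effect.

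2. *It is a labelling matter.* The quantity has clearance units, and the parent's CL/F is also scaled by an unmeasured F. This stands in part. To say the result is not a clearance at all would go too far. But the label CL/F declares only F, while the metabolite value also carries fm and any presystemic formation.

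3. *Little depends on it.* PK reporting is descriptive, and no endpoint, dose rule or stopping criterion uses metabolite clearance. SAP 3.7 names Cmax and AUCs for its optional plots. Cmax and the AUCs are already planned for any metabolite, so ratios could be derived later. This stands and limits the severity. The flags and exclusions in SAP 3.6.4 do not help, because they test the terminal phase and not the analyte.

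A reader might infer three stronger claims that the documents do not support. The first is that the rule overstates metabolite CL/F by 1/fm. That needs single-dose AUC0-inf or steady-state AUCtau, molar units and no presystemic formation, and the SAP uses AUC0-inf after repeated dosing. The second is that Vz/F is inflated by the same factor, which fails when formation is rate-limiting. The third is that SAP 2.3.4 contradicts 3.6.4. Section 2.3.4 names the parent and does not rule out contingent metabolite parameters.

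**Conclusion.** The point holds as a minor one. As written, SAP 3.6.4 and protocol 7.4 would attach CL/F and Vz/F to any measured metabolite using the dose of a different compound, and the result cannot be interpreted under those names.

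No corrected metabolite value can be computed, and neither the size nor the sign of the error can be stated. The ranges in the working (0.31 to 2.06 under the SAP's rule for fm 0.3 to 0.9; 0.14 to 1.7 with first-pass formation for fm 0.1 to 0.9) show only that both directions are possible. They rest on assumed PK values and on domperidone's bioavailability as a stand-in for CIN-102.

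The point concerns which analyte the formulas cover. Which AUC suits the parent's own CL/F is a separate question.

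**What to change.** In SAP 3.6.4 and protocol 7.4, state that CL/F and Vz/F are calculated for deuterated domperidone only. For any measured metabolite, report Cmax, Tmax, the AUCs and T1/2. In place of CL/F and Vz/F, give the metabolite-to-parent ratios of AUCtau and Cmax in molar units, with the molecular weights stated. The accumulation ratios in SAP 3.6.4 use no dose term and can stay for both analytes.

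The cost is a sentence or two in each document and a small addition to the PK programming if a metabolite is assayed. No new samples or data are needed.

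### SAP 3.6.4 divides the Day 14 dose by AUC0-inf, which understates CL/F and Vz/F after repeat dosing; the second lambda-z flag and the QD accumulation ratio also need small corrections

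*SAP*

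**What the plan says.** SAP 3.6.4 has two parameter lists. The Day 1 list contains Cmax, Tmax and AUC0-12 only. The second list is derived "using measured plasma concentrations following the final dose of CIN-102 (AM of Day 14), if the data permit" and includes AUCtau, AUC0-t, AUC0-inf, lambda-z, half-life, CL/F and Vz/F.

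- **AUC0-inf:** "AUC from time 0 to infinity; calculated as $(AUC_{0-t} + C_{last}/\lambda_z", with no term for drug carried over from earlier doses.
- **CL/F:** "Apparent total plasma clearance after oral administration; calculated as $Dose/AUC_{0-inf".
- **Vz/F:** "Apparent volume of distribution during terminal elimination phase after oral administration; calculated as" dose over the product of lambda-z and AUC0-inf.
- **R_AUC:** an accumulation ratio "after the first dose and last dose; calculated as" Day 14 AUCtau over Day 1 AUCtau.
- **Second lambda-z flag:** raised when "the terminal elimination rate constant indicates a positive slope", followed in brackets by the inequality lambda-z > 0. Flagged lambda-z values and their derived "parameters will be listed but excluded from statistical analysis".

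Protocol 7.4 names the parameters without formulas, so the SAP definitions govern. SAP 3.6.3 expects steady state to be confirmed from troughs. SAP 3.2 has two BID arms and one QD arm; the protocol (Synopsis and 9.2.4) lists three BID arms.

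**The concern.** Dose over AUC0-inf equals CL/F after a single dose. After the last of many doses, AUC0-inf also counts what earlier doses left behind, while the numerator is still one dose. The quotient therefore falls below CL/F, and Vz/F falls by the same factor. Day 1 yields no clearance, so this is the study's only clearance estimate.

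Multiple-dose pharmacokinetics is one of the three objectives in Protocol 2.1, and Protocol 1.3 says the results will inform later dose selection. Anyone who used this CL/F to predict average steady-state concentration would predict too high. Because the bias depends on the dosing interval, arms with different intervals and identical true clearance would show different values.

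Two further lines in the same section do not work as printed. The second flag contradicts the half-life formula, and R_AUC calls for a Day 1 AUCtau that the Day 1 list supplies only where the interval is 12 h.

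**Working it through.** The documents give no clearance, half-life or AUC value, so there is no plan figure to reproduce.

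**Inputs from the documents.** The profile follows the AM dose of Day 14 (SAP 3.6.4). This gives 13 × 2 + 1 = 27 doses for BID and 14 for QD. The interval tau is 12 h (BID) or 24 h (QD).

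**Assumptions.** Linear pharmacokinetics; half-life T from 5 to 12 h; one compartment with fast absorption.

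**Step 1: the correct area.** At steady state, AUCtau equals the single-dose AUC0-inf, which is F × Dose / CL. Dose/AUCtau therefore returns CL/F.

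**Step 2: the SAP's area.** Summing the remaining area of every dose, with k = ln(2)/T:

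AUC0-inf (last dose) = AUCtau / (1 − e^(−k × tau))

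so SAP CL/F ÷ true CL/F = 1 − 2^(−tau/T). Vz/F has the same ratio, since lambda-z itself is unchanged.

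**Step 3: numbers.**

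| T (assumed) | BID ratio | QD ratio | BID ÷ QD |
|---|---|---|---|
| 5 h | 1 − 2^(−2.4) = 0.811 | 1 − 2^(−4.8) = 0.964 | 0.841 |
| 7 h | 0.695 | 0.907 | 0.766 |
| 10 h | 0.565 | 0.811 | 0.697 |
| 12 h | 1 − 2^(−1) = 0.500 | 1 − 2^(−2) = 0.750 | 0.667 |

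The understatement is 19% to 50% for BID and 4% to 25% for QD. With equal true clearance, BID would read 16% to 33% below QD. Average steady-state concentration predicted from the BID value would be 1/0.811 = 1.23 to 1/0.500 = 2.00 times too high.

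**Step 4: sensitivity.**
- Wider half-life range: at 4 h the ratios are 0.875 (BID) and 0.984 (QD); at 24 h, 0.293 and 0.500. At 2 h the BID ratio is 1 − 2^(−6) = 0.984, so the bias nearly vanishes.
- First-order absorption (ka = 1/h), T = 8 h: 0.626 and 0.865, against 0.646 and 0.875 with fast absorption.
- Biexponential decline (fast phase 2 h, terminal phase 10 or 16 h): 0.43 to 0.78 (BID) and 0.67 to 0.92 (QD).
- Dose/AUCtau in the one-compartment superposition, for 4 to 24 h: 1.000 of true CL/F (0.9999 at 24 h).

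**Step 5: second flag.** Lambda-z is minus the slope of log concentration on time. Half-life is ln(2)/lambda-z, so every usable lambda-z is positive. The printed inequality flags all of them; the words before it, read as a rising regression line, flag none. On 1000 simulated declining profiles the two readings excluded 1000 and 0.

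**Step 6: R_AUC.** For BID, tau is 12 h, so Day 1 AUC0-12 is AUCtau and the ratio is defined. For QD, tau is 24 h and the Day 1 list has no 24-h area, so the denominator is missing.

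**The case against.** **The size is unknown and may be small.** This stands. Protocol 1.4 offers the only exposure data: mean Cmax 48.18 ng/mL at 60 mg BID (48.18/60 = 0.803 per mg) and 96.8 ng/mL after a single 120 mg dose (96.8/120 = 0.807 per mg). In the one-compartment, fast-absorption model, Cmax would accumulate by the same 1.23 to 2.00 factor, so near-equal values hint at little accumulation. They do not settle it: the doses differ and the day of the BID value is not given. Cmax can also hide a slow tail. With 90% of the initial concentration in a 2 h phase and 10% in a 10 h phase, BID Cmax rises only to 0.9/(1 − 2^(−6)) + 0.1/(1 − 2^(−1.2)) = 0.914 + 0.177 = 1.09 times the single-dose value, while the CL/F ratio is 0.778.

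**The regimen contrast depends on the QD arm.** This also stands. Only the SAP has that arm. With three BID arms the bias remains but is shared.

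**Little depends on CL/F.** Largely true. Parameters are summarised descriptively, no between-arm test of clearance is planned, and SAP 3.7 names Cmax and AUCs for its optional plots. No efficacy or sample-size result is touched, and clearance can be recomputed later from the same data.

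**A reader might infer that the flag would empty the terminal-phase tables.** The documents do not support that as a realistic outcome. The verbal part of the rule shows the intent, SAP 3.6.4 withholds these parameters only where the terminal phase is unacceptable, flagged values are still listed, and SAP 5.1 has the parameters calculated in both SAS and WinNonlin. It is a sign slip.

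**A reader might infer that R_AUC in the QD arm will be a 24-h area over a 12-h area.** The SAP specifies AUCtau on both days, not that mixture. What is missing is the Day 1 quantity.

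**Conclusion.** The CL/F and Vz/F formulas are wrong for a repeat-dose profile and bias both parameters downward. The direction follows from linear pharmacokinetics and needs no assumption about half-life. The size does: the ranges in the working hold only for the assumed 5 to 12 h and one compartment, and shorter half-lives would give less. A spurious clearance difference between regimens arises only if the once-daily arm is run; the SAP and protocol must be reconciled on the regimens in any case. Cmax, Tmax, AUCtau and troughs are sound.

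The flag is a sign slip to correct, because an exclusion rule should not contradict the half-life formula beside it. The R_AUC point is a missing definition for one arm. These corrections should be made before the PK analysis, but they do not threaten the trial's other conclusions.

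**What to change.** In SAP 3.6.4:

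1. For Day 14, define CL/F = Dose/AUCtau and Vz/F = Dose/(lambda-z × AUCtau).
2. Reword the second flag as a positive regression slope (lambda-z ≤ 0).
3. For R_AUC in the QD arm, use the same interval on both days, for example AUC0-12 on Day 14 over AUC0-12 on Day 1. A 24-h area on both days would serve only if Day 1 sampling supports it; the sampling times are redacted, and Protocol Table 2 schedules no PK sample on Day 2.

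The cost is a few lines of SAP text and the matching program changes, with no new samples. AUCtau is already planned from the same profile. One gain is that CL/F would no longer depend on lambda-z, so subjects would not drop out of its summary through the flag for more than 20% extrapolated area. Vz/F would still need an acceptable lambda-z.
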